8. RESEARCH QUESTION AND OBJECTIVES

The research question is: Are prescribers in France adherent to the recommendations and limitations for use described in the tofacitinib aRMM materials?

The primary objectives are to:

- 1. Describe the characteristics of patients treated with tofacitinib and by indication (i.e., RA, PsA and UC; off-label use), in terms of:
 - Demographics (e.g., age and sex);
 - Comorbidities and prior and current medication use.
- 2. Evaluate prescribers' adherence to the tofacitinib aRMMs for treating patients with RA, PsA or UC, specifically:
 - Adherence to the recommended posology per indication (average daily dose [ADD]) and duration of use;
 - Adherence to recommendations for patient screening and laboratory monitoring prior to and during tofacitinib treatment;
 - Adherence to recommendations for limitations of use, including:
 - Contraindicated use;
 - Use with medications not compatible with tofacitinib.

- Describe prescribing patterns over time:
 - Describe changes in the utilisation of tofacitinib following the updated recommendations and limitations for use implemented after the 2019 Article 20 referral and the 2021 signal evaluation procedure, specifically:
 - Use in patients with risk factors for VTE;
 - Use in patients aged 65 years and older;
 - Use in patients with risk factors for CV;
 - Use in patients with risk factors for malignancy.
 - Describe changes in the utilisation of tofacitinib following the updated recommendations and limitations for use implemented after the JAKi 2022/2023 Article 20 referral, specifically:
 - UC maintenance treatment dosage for patients with CV and malignancy risk factors, in addition to VTE risk factors.

9. RESEARCH METHODS

9.1. Study design

This is a retrospective cohort study to provide real-world evidence on the utilisation of tofacitinib in France.

The study presents a number of strengths, which include the prospectively collected electronic health data, the richness of data available in the Système National des Données de Santé (SNDS) and near-complete coverage of the French population (>99%) with minimal loss to follow-up.

9.2. Setting

The study population will be sourced from the French SNDS database. SNDS contains healthcare utilisation data, including pharmacy data, with a coverage of 99% of the population in France. Further details about this data source are provided in Section 9.4. The study population will consist of patients of all ages who newly initiated to facitinib in French routine clinical setting.

See Figure 1 for an overview of the study observation period (Section 9.2.3), including the indexing period, the VTE Reporting Periods 1-3 (Section 9.2.4), the CV and Malignancy Reporting Periods 1-3 (Section 9.2.5) and the JAKi Reporting Periods 1-3 (Section 9.2.6).

[figure not shown]

Figure 1. Overview of the study observation period

9.2.1. Inclusion criteria

Patients must meet all of the following inclusion criteria to be eligible for inclusion in the study:

- Have their first reimbursed prescription of tofacitinib (Anatomical Therapeutic Chemical [ATC] code L04AA29) during the indexing period;
- Have 12 months of available medical history *prior to* the index tofacitinib dispensing; and
- Have 12 months of available medical data *after* the index tofacitinib dispensing.

9.2.2. Exclusion criteria

Patients meeting any of the following criteria will not be included in the study:

[figure not shown]
- Have ≥1 reimbursed prescription of tofacitinib in the 12 months prior to the indexing date; or
- Patients with an index tofacitinib reimbursed prescription for an approved indication for which the original aRMM materials for that indication were not yet distributed or for an approved indication not examined as part of this study (i.e., ankylosing spondylitis and juvenile idiopathic arthritis).
 - For example, if a patient indexes with a tofacitinib reimbursed prescription for UC in France prior to May 2019 (the date of full distribution of the original aRMM materials for UC indication), he or she will be excluded from the study.

^{*}Aligned with the first reimbursed prescription record in the French database

9.2.3. Study period

The study period will be from 01 January 2017 to 31 December 2025. The **indexing period** will begin on 01 January 2018 (the earliest date of the full distribution of the original aRMM materials for France [RA], aligned with the first reimbursed prescription record in the French database), will end on 31 December 2024, and will be used to identify patients who newly initiated tofacitinib. The date of a patient's first reimbursed prescription of tofacitinib during the indexing period will be considered the patient's **index date** (Figure 2).

Figure 2. Example index tofacitinib dispensing and patient-specific study period against the Venous Thromboembolism Reporting Periods

^{*} Aligned with the first reimbursed prescription record in the French database

The 12-month **baseline period** will immediately precede the index date and will be used to ascertain indication (including off-label use), comorbidities, prior and current medications, potential contraindicated use of tofacitinib, VTE risk factors, CV risk factors, malignancy risk factors, use in patients aged 65 years and older and whether there is evidence that prescribers are following the recommended screenings in the aRMM materials that should occur *prior to* initiation of tofacitinib.

The 12-month **follow-up period** will begin on the patient's index date. Variables that will be ascertained during the follow-up period include comorbidities, comedications, adherence to the recommended posology per indication (ADD) and duration of tofacitinib treatment, potential contraindicated use of tofacitinib, VTE, CV or malignancy risk factors, use with concomitant medications not compatible with tofacitinib and whether there is evidence that prescribers are following the recommended monitoring in the aRMM materials that should occur *after* initiation of tofacitinib.

[figure not shown]
9.2.4. Venous Thromboembolism Reporting Periods

For analyses evaluating changes in the use of tofacitinib in patients with VTE risk factors, the indexing period will be split into the following 3 periods:

- **Reporting Period 1**, which will cover the 17-month period after the initial distribution of the aRMM materials but *prior to* the PRAC/CHMP's notification of an increased risk of VTE among patients already at high risk (01 January 2018 through 31 May 2019, to allow for dissemination of DHPC letters following announcement of the provisional measures);
- Reporting Period 2, which will cover the 17-month period after the PRAC/CHMP's notification of an increased risk of VTE and mortality, through initial distribution and uptake of the 2019 Article 20 referral aRMM materials (01 June 2019 through 31 October 2020); and
- **Reporting Period 3**, which will cover the 50-month period after the period of initial distribution and uptake of the 2019 Article 20 referral aRMM materials (01 November 2020 through 31 December 2024).

See Figure 3 for an overview of the VTE Reporting Periods 1-3.

Figure 3. Overview of the Venous Thromboembolism Reporting Periods

^{*}Aligned with the first reimbursed prescription record in SNDS

[figure not shown]

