France	RA	September 2017	January 2018	04 May 2020	17 May 2022	06 April 2023
	PsA	December 2018	May 2019			
	UC	February 2019	May 2019			

A comprehensive plan was proposed to assess the effectiveness of the aRMM programme, which consists of the following 2 components:

- 1. Process indicators (i.e., HCPs' receipt and understanding of the aRMM materials); and
- 2. Outcome indicators (i.e., prescribing and clinical practice behaviours with respect to recommendations).

To assess these 2 components, the MAH proposed the following post-authorisation safety studies with the aim of evaluating the effectiveness of the aRMM programme:

- 1. A survey of tofacitinib prescribers to address component 1 (A3921334, completed); and
- 2. A drug utilisation study (DUS) (Study A3921321) to address component 2 that will assess prescribing patterns of tofacitinib and whether prescribers are adherent to the screening and monitoring recommendations and limitations for use included in the aRMM materials for patients prescribed tofacitinib.

As a result of the Article 20 benefit-risk reassessment, the MAH will additionally evaluate HCPs' adherence to the new PRAC recommendations and limitations for use to minimise the risk of VTE across all approved indications (i.e., tofacitinib should be used with caution in patients with known VTE risk factors regardless of indication and dosage), with additional focus on the use of tofacitinib 10 mg BID as a maintenance treatment for patients with UC, and use and prior treatments among patients aged 65 years and older treated with tofacitinib. The MAH will also examine tofacitinib prescribing patterns over time, as well as changes in the utilisation of tofacitinib among patients with VTE risk factors and among elderly patients aged \geq 65 years following the updated recommendations and limitations for use. As a result of the 2021 signal evaluation procedure, the MAH will also assess HCPs' adherence to the

new EMA recommendations and limitations for use related to tofacitinib use in patients with CV risk factors and use in patients with malignancy risk factors. Similar to above, the MAH will also examine tofacitinib prescribing patterns over time in the context of the 2021 signal evaluation procedure outcome. As a result of the 2022/2023 JAKi Article 20 referral, the MAH will assess HCPs' adherence to the updated recommendations and limitations for use related to tofacitinib use in patients with VTE, CV or malignancy risk factors.

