9.5. Study size

Comparative analyses for the changes in the proportions of patients with risk factors

For the comparative analyses, the study will assess changes in the proportion of tofacitinib initiators with risk factors of interest (e.g., VTE, elderly, CV, and malignancy) over different reporting periods (Section 9.2.4-9.2.6). The primary comparison of interest will be the proportion of tofacitinib initiators with risk factors during reporting period 3 (when full implementation of the updated aRMMs is expected) against that during reporting period 1 (baseline before implementation or notification of updated aRMMs). Secondary comparisons

b Data are updated once a year, usually by the end of August

of interest will be between reporting period 1 and reporting period 2, as well as reporting period 2 and reporting period 3 to assess any intermediate changes.

Sample size required for evaluating changes in the proportion of patients with risk factors across reporting periods was calculated using the following formula based on two independent sample *z*-test for proportions:⁸

$$N= \frac{(z_{\alpha/2}+z_{\beta})^2(p_1(1-p_1)+p_2(1-p_2))}{\epsilon^2}$$

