Preliminary data from the first interim report of the ongoing DUS study (A3921321) suggests that 30 to 80% of tofacitinib initiators had one or more risk factors of interest at baseline (e.g., during reporting period 1). Sample size was calculated across a range of possible baseline proportions and meaningful differences between any two reporting periods. Given the challenges in defining minimum meaningful differences and the lack of scientific guidance or validated thresholds, Chen et al.'s rule of thumb for classifying the magnitude of effect size based on odds ratios (OR) (e.g., small effect) is used to inform the minimum meaningful difference. Minimum sample size is determined based on the smallest sample size needed to detect a minimum meaningful difference per scenario of baseline proportion. It is thus estimated that 160 to 354 patients per reporting period (480 to 1,062 total patients) per indication group (e.g., RA/PsA and UC) are needed to detect a minimum meaningful difference with 80% statistical power ($\beta = 0.20$) and a two-sided 5% significance level ($\alpha = 0.05$) (Table 1**Error! Reference source not found.**). Sample size needed varies based on the baseline proportion and point percent difference between reporting periods. The required sample size is irrespective of the length of the reporting period.

Table 5.	Sample size for comparing changes in the proportion of patients with risk
	factors of interest across reporting periods

Percentage of patients with at least one risk factors at baseline	Point percent difference between any two reporting periods	Effect size classification for the difference based on OR ^a	Number of patients needed per reporting period ^b	Total number of patients needed for the entire study period per indication group b, c
80%	10%	Small	291	873
70%	10%	Small	354	1,062
70%	15%	Small	160	480
60%	10%	Small	385	1,155
60%	15%	Small	171	513
50%	10%	Small	385	1,155
50%	15%	Small	167	501
40%	10%	Small	354	1,062
30%	10%	Small	291	873

Odds ratio = VTE reporting period X odds of outcome / VTE reporting period Y odds of outcome; Classified effect sizes as weak ($1 \le OR < 1.5$), small ($1.5 \le OR < 2$), medium ($2 \le OR < 3$) and large (≥ 3).

Comparative analyses for the changes in composite risk factor scores

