Based on these estimated numbers of patients during the entire study period and sample size calculation, the study is anticipated to have sufficient sample size to detect meaningful differences in the use of tofacitinib among patients with risk factors between the pre- and post-implementation period of updated aRMMs. All eligible patients during the study period will be included in the analysis. The number of patients will be actively monitored during the course of the study and the MAH will provide timely notification to the EMA if sufficient sample size is not reached during the planned study period.

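### UC and PsA can enter VTE Reporting Period 1 for at most one month, so the primary Period 3 vs Period 1 comparison lacks its stated power in UC and mixes indications in RA/PsA

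*Protocol*

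**What the plan says.** - **Who can enter.** Section 9.2.2 excludes a patient whose index prescription is "for an approved indication for which the original aRMM materials for that indication were not yet distributed". Its example is UC: a patient is excluded if indexed "prior to May 2019 (the date of full distribution of the original aRMM materials for UC indication").
- **Dates.** Table 2 (Section 7) gives January 2018 for RA and May 2019 for UC. PsA shares the May 2019 date: "PsA December 2018 May 2019" are its reimbursement and distribution dates.
- **Periods.** Section 9.2.4 defines VTE Period 1 for all indications as "01 January 2018 through 31 May 2019, to allow for dissemination of DHPC letters following announcement of the provisional measures" and describes it as 17 months. Period 2 is also 17 months, and Period 3 runs 50 months from November 2020.
- **Comparison.** Section 9.5: "The primary comparison of interest will be the proportion of tofacitinib initiators with risk factors during reporting period 3", set against Period 1. Contrasts involving Period 2 are secondary.
- **Size.** For proportions, 160 to 354 patients per period in each indication group (RA/PsA and UC), with 80% power, two-sided 5% and equal period sizes. It adds: "The required sample size is irrespective of the length of the reporting period". For the composite score the figure is 80 to 142 per period.
- **Conclusion.** From projected totals of 8,000 RA or PsA and 2,000 UC, Section 9.5 states that "the study is anticipated to have sufficient sample size to detect meaningful differences in the use of tofacitinib among patients with risk factors".

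**The concern.** The exclusion rule and the period boundary were each set for their own reason, and together they leave almost no VTE baseline for two of the three indications. In UC, a non-significant Period 3 vs Period 1 result would say little, because the baseline is nearly empty. Yet Section 9.5 would let a reader take it as an 80%-powered finding of no change.

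In the pooled RA/PsA group numbers are not the difficulty. Period 1 is almost entirely RA and Period 3 is RA plus PsA. If risk-factor prevalence differs between the two diseases, the pooled proportion moves without any change in prescribing, and that movement could be credited to the revised materials.

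The part of the age 65 and over analysis that uses the VTE periods (9.7.2.4.2) inherits both problems. By contrast, UC and PsA have 26 eligible months in Period 1 of the CV/malignancy series (May 2019 to June 2021) and 47 in that of the JAKi series (May 2019 to March 2023), so the near-empty baseline does not arise there.

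**Working it through.** **1. The plan's own figures.** The Section 9.5 formula is N = (1.960 + 0.842)² × [p1(1−p1) + p2(1−p2)] / d², with p2 = p1 − d. It reproduces all nine rows of Table 5. For example, 70% to 55% gives 7.849 × (0.2100 + 0.2475) / 0.0225 = 159.6, so 160. The arithmetic is sound. The problem is its application to a period that is nearly empty for UC.

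**2. UC numbers by period.** The protocol gives about 1,000 UC starters from January 2018 to December 2020 and 2,000 by December 2024, with no monthly counts. Even accrual is therefore an assumption, and three readings of the first figure are used:

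| The 1,000 spread over | Per month | Period 1 (1 month) | Period 2 (17 months) | Period 3 (2 months + 1,000) |
|---|---|---|---|---|
| 36 months, January 2018 on | 27.8 | 28 | 472 | 1,056 |
| 23 months, from reimbursement (February 2019) | 43.5 | 43 | 739 | 1,087 |
| 20 months, from eligibility (May 2019) | 50.0 | 50 | 850 | 1,100 |

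Spreading 2,000 over the 68 eligible months gives 29 per month, inside this range. Table 2 gives only the month for May 2019, so one month is an upper limit.

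**3. Power of Period 3 vs Period 1 in UC.** Power = Φ(d/SE − 1.960), with SE² = p1(1−p1)/n1 + p2(1−p2)/n3. For 70% to 60% with 50 and 1,100 patients: SE = √(0.21/50 + 0.24/1,100) = 0.0665, and Φ(1.504 − 1.960) = 32%. The last column is the Period 1 size needed for 80% power when Period 3 has 1,087.

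| Baseline, drop | Table 5 N | Power, n1 = 28 | n1 = 43 | n1 = 50 | n1 needed |
|---|---|---|---|---|---|
| 80%, 10 | 291 | 25% | 36% | 40% | 149 |
| 70%, 10 | 354 | 20% | 29% | 32% | 200 |
| 70%, 15 | 160 | 40% | 56% | 62% | 80 |
| 60%, 10 | 385 | 18% | 26% | 29% | 230 |
| 60%, 15 | 171 | 36% | 51% | 56% | 91 |
| 50%, 10 | 385 | 18% | 25% | 28% | 238 |
| 50%, 15 | 167 | 35% | 49% | 55% | 95 |
| 40%, 10 | 354 | 18% | 26% | 29% | 223 |
| 30%, 10 | 291 | 21% | 29% | 33% | 187 |

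The difference detectable with 80% power is about 16 to 27 points, against the planned 10 to 15.

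**4. Composite score, same sizes (28, 43, 50).** SD 0.9 and difference 0.40: 64%, 82%, 87%. SD 0.8 and 0.35: 62%, 81%, 86%. SD 0.8 and 0.30: 50%, 68%, 74%. SD 0.6 and 0.20: 41%, 58%, 64%.

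**5. RA/PsA mix.** Let s be the PsA share of steady-state starts. With one eligible month in 17, its Period 1 share is (s/17) / (s/17 + 1 − s). For assumed s of 10%, 20% and 30% this is 0.6%, 1.4% and 2.5%. If RA and PsA differ by an assumed 10 to 20 points in prevalence, the shift is (s − Period 1 share) × gap: from 0.094 × 10 = 0.9 points to 0.275 × 20 = 5.5 points. With no PsA at all in Period 1, the top of that range is 0.30 × 20 = 6 points.

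**6. Period 3 vs Period 2 in UC.** With the sizes in step 2, the lowest power for a 10-point drop is 95% (50% to 40%, 472 vs 1,056).

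**The case against.** Several counter-arguments have force:

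- **Unequal allocation.** Setting 28 to 50 against 160 to 354 overstates the gap, because those figures assume equal periods. With Period 3 near 1,087 the rows behind 160 to 354 need about 80 to 223 (230 and 238 for the two rows at 385). The shortfall is smaller but remains in every row.
- **Composite score.** Section 9.7.2.4.1 adds it to gain power, and some scenarios pass 80%. It does not rescue the claim for proportions.
- **Stratification.** Section 9.7 allows results by approved indication, and model details may sit in the SAP. An RA-only stratum would remove the mix problem. But the protocol does not require one for this contrast, and its sample size and abstract use the pooled group.
- **Monitoring.** Section 9.5 undertakes to watch numbers and notify the EMA. A VTE Period 1 that closed in 2019 cannot gain patients.

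Two stronger readings are tempting but unsupported. A reader might infer that UC maintenance dosing is unobserved for Period 1, since week 17 of a 1 May 2019 starter falls in August 2019. Section 9.2.4 splits the indexing period, so patients belong to a period by index date and their own follow-up counts wherever it falls; no data are missing. A reader might also infer that UC in JAKi Period 2 is inadequate because about 104 patients (1,000/48 × 5 months) is below 160. That 160 again assumes equal allocation. For 70% to 55%, power with 104 is about 81% against 333 in Period 3 and 84% against about 980 in Period 1. The contrast is secondary, and the JAKi outcome is maintenance dose, which Table 5 does not size.

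**Conclusion.** The point stands for the VTE reporting periods. That UC and PsA have at most one eligible month in Period 1 follows from the protocol's dates alone. The size of the UC shortfall rests on even accrual: about 28 to 50 patients, and power of about 18% to 40% for 10-point and 35% to 62% for 15-point differences in proportions. No reading of the accrual figures reaches the stated 80% for any Table 5 row. The composite score is less affected, at about 41% to 87% in the scenarios checked.

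The change of case mix in the pooled RA/PsA contrast is certain in kind but not in size. The protocol gives neither the PsA share nor separate prevalences, so the 1 to 6 points are illustration only, and the direction depends on which disease has the higher prevalence. RA on its own keeps its full 17-month baseline.

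**What to change.** 1. In Section 9.5, replace the sufficiency statement with expected numbers per indication and reporting period. State that UC Period 3 vs Period 1 for the VTE periods does not reach 80% power for the Table 5 differences.
2. For UC, and for PsA alone, label VTE Period 1 descriptive in the VTE and age 65 and over analyses. Rely on the already planned Period 3 vs Period 2 contrast.
3. Run the RA/PsA VTE-period and age 65 and over contrasts in RA alone, or add an RA-vs-PsA term to the logistic and linear models.

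The cost is wording in Sections 9.5 and 9.7.2.4 and one stratum or model term; no further data are needed. There are two real downsides. The UC power statement becomes less favourable. And VTE Period 2 begins after the notification, so Period 3 vs Period 2 has no pre-notification baseline: it measures change after the revised materials, not before versus after, and the report should say so.

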9.2.5. Cardiovascular and Malignancy Reporting Periods

For analyses evaluating changes in the use of tofacitinib in patients with CV risk factors and patients with malignancy risk factors, the indexing period will be split into the following 3 periods:

- **Reporting Period 1**, which will cover the 42-month period after the initial distribution of the aRMM materials but *prior to* the PRAC/CHMP's notification of an increased risk of CV-related outcomes and malignancy-related outcomes among patients already at high risk (01 January 2018 through 30 June 2021, to allow for dissemination of DHPC letters);
- Reporting Period 2, which will cover the 16-month period of and after the PRAC/CHMP's notification of restrictions on use in the context of increased risk of CV-related outcomes and malignancy-related outcomes, through initial distribution and uptake of the 2021 signal evaluation procedure aRMM materials (01 July 2021 through 31 October 2022); and
- **Reporting Period 3**, which will cover the 26-month period *after* the period of initial distribution and uptake of the 2021 signal evaluation procedure aRMM materials (01 November 2022 through 31 December 2024).

See Figure 4 for an overview of the CV and Malignancy Reporting Periods 1-3.

Figure 4. Overview of the Cardiovascular and Malignancy Reporting Periods

^{*}Aligned with the first reimbursed prescription record in the French database

[figure not shown]
